#### **Nonserious Adverse Events**

A nonserious AE is defined as any untoward change in a subject's medical health that does not meet serious criteria noted below (e.g., is not life-threatening, does not require hospitalization, does not prolong a current hospitalization, is not disabling, etc.). All adverse events must be reported regardless of whether they are related to the study treatment or not.

For nonserious adverse events, an AEF containing all available information will be collected on a routine basis and submitted to the Medical Monitor before the close of the study.

#### **Serious Adverse Events**

A serious adverse event (SAE) is defined as any adverse experience that meets any of the following criteria:

- Results in death.
- Is life-threatening.

NOTE: Life-threatening means that the subject was at immediate risk of death from the reaction as it occurred, i.e., it does not include a reaction which hypothetically might have caused death had it occurred in a more severe form.

- Requires inpatient hospitalization or prolongation of existing hospitalization.

NOTE: In general, hospitalization signifies that the individual remained at the hospital or emergency ward for observation and/or treatment (usually involving

- an overnight stay) that would not have been appropriate in the physician's office or an out-patient setting. Complications that occur during hospitalization are AEs. If a complication prolongs hospitalization or fulfills any other serious criteria, the event is serious. When in doubt as to whether "hospitalization" occurred, the event should be considered serious.
- Results in persistent or significant disability/incapacity. Disability is defined as a substantial disruption of a person's ability to conduct normal life functions.  
NOTE: The term disability means a substantial disruption of a person's ability to conduct normal life functions. This definition is not intended to include experiences of relatively minor medical significance such as uncomplicated headache, nausea, vomiting, diarrhea, influenza, or accidental trauma (e.g., sprained ankle) which may interfere or prevent everyday life functions but do not constitute a substantial disruption.
  - Is an important medical event. An important medical event is an event that may not result in death, be life-threatening, or require hospitalization but may be considered an SAE when, based upon appropriate medical judgment, it may jeopardize the subject and may require medical or surgical intervention to prevent one of the outcomes listed in the definitions for SAEs. Examples of such medical events include allergic bronchospasm requiring intensive treatment in an emergency room or at home, blood dyscrasias or convulsions that do not result in subject hospitalization, or the development of drug dependency or drug abuse.  
All available information on a serious adverse event(s) and any other associated AE, if applicable, must be forwarded to the study coordinator for forwarding to the Medical Monitor immediately (i.e., within one working day of the Investigator's or site's knowledge of the event) as follows:
    - In studies utilizing EDC (electronic data capture), all available information for the SAE and any associated AE(s) must be entered immediately into the EDC system.
    - Additional information for any applicable event is to be reported as soon as it becomes available.

In addition to the reporting of serious adverse events to the study Medical Monitor, the SAE must be reported to the IRB/IEC according to their requirements.

The investigator must document all adverse device events (serious and nonserious but related) and all serious adverse events (related and unrelated) on the Adverse Device Effect and Serious Adverse Event Form. Any device quality complaints will also be documented.

- **Both the Quality Complaint Form and the Adverse Device Effect and Serious Adverse Event Form must be e-mailed immediately to the principal investigator at [[contact]](mailto:[contact]).**

- **Additional relevant information is to be reported as soon as it becomes available.**

#### 13.3.1 Intensity and Causality Assessments

For every adverse event and quality complaint, the investigator must assess the causality as Related or Not Related to the medical device under investigation. An assessment of causality will also be performed by the Medical Monitor utilizing the same definitions, as shown below:

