### 3. GENERAL INFORMATION

Objective	
The objective of the current study is to prospectively evaluate 3-month clinical outcomes from LASIK performed using the Phorcides surgical planning software with Contoura topography-guided ablation in both eyes of subjects with myopia and myopic astigmatism seeking refractive surgery for distance correction. Data will be compared to published results for wavefront optimized LASIK and LASIK performed with Contoura using other refractive algorithms.
 
The hypothesis is that use of the Phorcides planning software will result in a higher percentage of eyes with residual refractive cylinder <math>\leq 0.25D</math> than will be achieved with wavefront-optimized (WFO) LASIK. It is also expected that unaided postoperative visual acuity and visual symptoms will be improved.

Test Article(s)	Phorcides Analytical Engine refractive surgery planning software
Control Article(s)	None
Sample size	140 eyes of 70 subjects
Study Population	Subjects $\geq 20$ years of age with myopia and myopic astigmatism, who are suitable candidates for LASIK, meet the approved range of treatment for Contoura topography-guided LASIK and desire optimal uncorrected distance visual acuity in both eyes.
Number of sites	Four
Study Design	Prospective, single arm, open-label study.
Masking	None
Variables	Primary: 

● Residual refractive cylinder

 Secondary: 

● Monocular uncorrected distance visual acuity

- Monocular corrected distance visual acuity
- Residual refractive sphere
- Corneal aberrations
- Ocular aberrations (at sites equipped for such measurement)
- Subjective questionnaire evaluating visual symptoms such as light sensitivity glare, halos, and starbursts

Duration / Follow-up    Preoperative to 3 months postoperative

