## **8. STUDY DESIGN**

The study is a prospective, single-arm open clinical trial to evaluate residual refractive error and distance visual acuity after excimer laser treatment for the correction of refractive error to produce good uncorrected distance vision. All eyes enrolled will have surgery planned with Phorcides and treated using the Contoura topography-guided surgery algorithm.

Subjects will be assessed pre-operatively and at 1 day, 1 month and 3 months post-operatively.

Clinical evaluations at 1 month and 3 months will include measurement of uncorrected distance visual acuity (UCDVA), manifest refraction, and corrected distance visual acuity (CDVA). At 3 months, corneal aberrations will be measured, and subjects will complete a questionnaire evaluating satisfaction with their visual outcome, quality of vision, and visual symptoms (light sensitivity, difficulty driving at night, reading difficulty, fluctuation in vision, glare, halos, and starbursts).

The primary outcome measure will be the residual refractive cylinder.

Secondary outcome measures will be the following:

- Uncorrected distance visual acuity
- Residual sphere
- Corneal aberrations
- Ocular aberrations, at sites with the appropriate equipment to measure such.
- Satisfaction with the visual outcome, quality of vision, and visual symptoms (light sensitivity, difficulty driving at night, reading difficulty, fluctuation in vision, glare, halos, and starbursts).

Safety measures will be

- Change in corrected distance visual acuity
- Satisfaction with the visual outcome, quality of vision, and visual symptoms (light sensitivity, difficulty driving at night, reading difficulty, fluctuation in vision, glare, halos, and starbursts).

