### ***13.3. Procedures for Recording and Reporting AEs and SAEs***

Subsequent to signing an informed consent form, all untoward medical occurrences that occur during the course of the study must be documented on an Adverse Event Form (AEF). A separate AEF must be filled out for each event. When possible, signs and symptoms indicating a common underlying pathology should be documented as one comprehensive event. For each recorded event, the AE documentation must include the onset date, outcome, resolution date (if event is resolved), intensity (i.e., severity), any action with study treatment taken as a result of the event, and an assessment of the adverse event's relationship to the study treatment.

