#### ***Causality***

**Related** An adverse event or quality complaint classified as related may be either definitely related or possibly related where a direct cause and effect relationship with the medical device has not been demonstrated, but there is a reasonable possibility that the adverse event or quality complaint was caused by the medical device.

**Not Related** An adverse event or quality complaint classified as not related may either be definitely unrelated or simply unlikely to be related (i.e., there are other more likely causes for the adverse event or quality complaint).

Where appropriate, the investigator must assess the intensity (severity) of the adverse event as mild, moderate, or severe based on medical judgment with consideration of any subjective symptom(s), as defined below:

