#### ***13.5. Safety Analyses***

The type, severity, duration and frequency of reported ocular adverse events will be tabulated. Adverse events will also be summarized for events that were considered treatment-related.

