## **19. SUMMARY OF RISKS AND BENEFITS**

### ***19.1. Summary of risks***

The risks for LASIK surgery in this study (topography-guided or wavefront-optimized) are not different from the standard risks. The excimer laser system used in the study has been approved for topography-guided and wavefront-optimized refractive surgery. The most common side effects of laser refractive surgery are glare and halos, dry eye and residual refractive error.

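### Relatedness of adverse events is judged against three unreconciled referents, so procedure-caused events can be rated Not Related at one site and Related at another, which changes the treatment-related summary and the reporting route.

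*Combined protocol and SAP*

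**What the plan says.** Section 3 (General Information) names one test article: "Phorcides Analytical Engine refractive surgery planning software". Section 8 makes clear that software and surgery always come together: "All eyes enrolled will have surgery planned with Phorcides and treated using the Contoura topography-guided surgery algorithm".

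Relatedness then appears in four places:

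- Section 13.3 requires the record of each event to include its "relationship to the study treatment". Study treatment is not defined and no rating categories are given here.
- Section 13.3.1 states that for every event and quality complaint "the investigator must assess the causality as Related or Not Related to the medical device under investigation". The Medical Monitor rates with the same definitions. An event is Related if "there is a reasonable possibility that the adverse event or quality complaint was caused by the medical device", which includes possibly related events. It is Not Related if it is definitely unrelated, or unlikely to be related because "there are other more likely causes for the adverse event or quality complaint".
- Section 13.5 gives two outputs. The first is a tabulation of all reported ocular events. The second is described thus: "Adverse events will also be summarized for events that were considered treatment-related".
- Section 18.3 ends a patient's participation for a severe event that may be related to the study, a third referent.

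The serious-event reporting text within Section 13.3 adds a form that depends on relatedness. Serious events go on the Adverse Device Effect form whether related or not, but nonserious events only if related. That form is to be e-mailed immediately. Other nonserious event forms are due before the close of the study.

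**The concern.** The one scale with definitions points at the investigational device, and the one listed test article is software that plans the ablation. No category covers the LASIK procedure, the flap or the excimer laser. Section 19.1 attributes the expected effects to the surgery: "The most common side effects of laser refractive surgery are glare and halos, dry eye and residual refractive error". A site that takes the device to be the software, and applies the more-likely-cause clause, can properly rate a flap event or dry eye Not Related. A site that takes the referent to be the whole treatment would rate it Related. Both would be following the text.

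At stake is the meaning of the treatment-related summary across four sites, and the route and timing by which nonserious events are reported. A single binary rating also cannot distinguish an event caused by the software's plan from one caused by the surgery. With a single arm and every eye receiving both, an event-level causality judgement is the only means the plan has of trying to make that distinction.

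**Working it through.** No arithmetic applies. The plan states no figure on this point, and the question is what each use of *related* refers to.

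**Step 1: the referents side by side.**

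| Section | Referent | Categories defined? | Used for |
|---|---|---|---|
| 13.3 | Study treatment | No | Record of each event |
| 13.3.1 | Investigational device | Yes | Investigator and Medical Monitor ratings |
| 13.3, serious-event reporting | Related, on a form titled for device effects | No | Whether a nonserious event goes on that form |
| 13.5 | Treatment | No | Second safety output |
| 18.3 | The study | No | Ending a patient's participation |

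That makes three referents (device, treatment, study). One has definitions, and no section maps one to another.

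**Step 2: what the device is.** The plan does not define it. Section 3 lists only the software as test article, and Section 19.1 describes the laser system as already approved. Software-only is therefore a reasonable inference, but it is not stated.

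**Step 3: one nonserious dry-eye event under each reading.**

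| Reading by the site | Device rating (13.3.1) | Study-treatment rating (13.3) | In the 13.5 treatment-related summary? | On the Adverse Device Effect form? |
|---|---|---|---|---|
| Device is the software; the same answer is used for study treatment | Not Related | Not Related | No | No |
| Device is the software; study treatment is Phorcides-planned LASIK | Not Related | Related | Yes, if 13.5 uses the 13.3 rating; no, if it uses 13.3.1 | No, if the form follows the device rating |
| Both are Phorcides-planned LASIK | Related | Related | Yes | Yes |

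The same event can thus be handled in several ways, each consistent with the text. A nonserious flap event follows the same rows.

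**Step 4: events for which the split is weaker.** Residual refractive error, and arguably halos, could reasonably be put down to the plan that the software produced. The possibly-related limb of the definition would then make them Related even on the software-only reading. The argument is strongest for flap events and dry eye.

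**Step 5: what does not depend on relatedness.** Section 13.3 requires all adverse events to be reported whatever their relation to treatment. The first output of Section 13.5 has no causality filter. The safety measures in Section 8 (change in corrected acuity, and the questionnaire on satisfaction, vision quality and symptoms) do not use a causality rating either.

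**The case against.** The strongest opposing case is that the plan already asks for the right judgement. Section 13.3 requires a study-treatment assessment for every event, and Section 13.5 uses matching language rather than device language. Section 13.1 speaks of a subject being given a study treatment, which suits surgery better than planning software, and Section 8 describes the intervention as Phorcides-planned Contoura LASIK. On that reading dry eye and flap events stay in the treatment-related summary.

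This stands as far as it goes. A reader might infer from Section 13.3.1 that causality is judged solely against the software and that LASIK-caused events necessarily drop out of the treatment-related summary. The documents do not support that. A second assessment is required, the device is never defined as the software alone, no section says the device rating feeds the summary, and possibly related events count as Related. A reader might also infer that the safety of the procedure would go undescribed. That fails too, because the unfiltered ocular table and the Section 8 measures remain.

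The objection does not remove the ambiguity. Study treatment is undefined, the only categories available for rating it are written for the device, and the Medical Monitor uses the same definitions, so central review would not settle which referent was meant.

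It can also be said that defining the terms would suffice, and that a separate plan rating has no comparator to test it. Definitions would indeed settle what the summary contains. They would not let one binary rating separate plan-caused from procedure-caused events. The separate rating would remain a descriptive clinical judgement, and should be presented as such.

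**Conclusion.** The concern holds as an inconsistency that should be corrected. Relatedness has three unreconciled referents, and procedure-caused events, flap events and dry eye above all, can be rated Not Related on a reading that the text permits. They may then be left out of the treatment-related summary and, if nonserious, off the Adverse Device Effect form.

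The effect is confined to that summary and to the reporting route and timing. It does not touch the primary outcome, the requirement to report all events, or the unfiltered ocular table. The documents give no adverse event rates, so the number of events that could move cannot be stated.

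The conclusion rests on two assumptions: that at least some sites would read the device as the listed test article, and that the adverse event form, which is not in the documents, does not already ask separate causality questions. If it does, only the text needs aligning.

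**What to change.** - In Section 13.3.1 and on the adverse event form, rate each event Related or Not Related twice: (a) to the LASIK procedure, including flap and excimer ablation, and (b) to the Phorcides-generated plan. The Medical Monitor does the same.
- In Section 13.5, define treatment-related as related to (a) or (b), and tabulate (b) separately.
- Use the same terms in the event record in Section 13.3 and in the text on the Adverse Device Effect form, stating which rating decides whether a nonserious event goes on that form.
- Reconcile the referent in Section 18.3 with these terms. Which rule should apply there is for the sponsor and investigators to decide.

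The cost is one extra tick box, a few sentences, and possibly more events counted as treatment-related. The change should be made before sites begin coding events, since separate ratings are hard to reconstruct afterwards.

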#### ***Causality***

**Related** An adverse event or quality complaint classified as related may be either definitely related or possibly related where a direct cause and effect relationship with the medical device has not been demonstrated, but there is a reasonable possibility that the adverse event or quality complaint was caused by the medical device.

**Not Related** An adverse event or quality complaint classified as not related may either be definitely unrelated or simply unlikely to be related (i.e., there are other more likely causes for the adverse event or quality complaint).

Where appropriate, the investigator must assess the intensity (severity) of the adverse event as mild, moderate, or severe based on medical judgment with consideration of any subjective symptom(s), as defined below:

#### ***Intensity (Severity)***

**Mild** An adverse event is mild if the subject is aware of but can easily tolerate the sign or symptom.

Moderate	An adverse event is moderate if the sign or symptom results in discomfort significant enough to cause interference with the subject's usual activities.
Severe	An adverse event is severe if the sign or symptom is incapacitating and results in the subject's inability to work or engage in their usual activities.

The investigator must document any action taken (i.e., medication, intervention, or treatment plan) and outcome of the adverse event or quality complaint when applicable.

#### ***13.4. Follow-Up of Adverse Events and Quality Complaints***

The investigator is responsible for providing adequate and safe medical care to subjects during the study and for ensuring that appropriate medical care and relevant follow-up procedures are maintained after the study. Any additional data from these follow-up procedures must be documented and available to the study coordinator who, with the Medical Monitor, will determine when the data need to be documented on the CRFs.

#### ***13.5. Safety Analyses***

The type, severity, duration and frequency of reported ocular adverse events will be tabulated. Adverse events will also be summarized for events that were considered treatment-related.

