## **10. ANALYSIS PLAN**

### **10.1. *Analysis Data Sets***

All subjects who are enrolled in the study will be evaluated for safety. Efficacy analyses will be performed based on data from those eyes for which uncomplicated LASIK was completed.

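### Section 13.5 plans no result for non-ocular adverse events judged not related, and no output that identifies any event as serious

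*Combined protocol and SAP*

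**What the plan says.** Collection is broad. Section 13.3 requires a form for every untoward occurrence after consent, and its part on nonserious events states: "All adverse events must be reported regardless of whether they are related to the study treatment or not". The part on serious events requires documentation of "all serious adverse events (related and unrelated) on the Adverse Device Effect and Serious Adverse Event Form", and adds that "the SAE must be reported to the IRB/IEC according to their requirements". Section 10.1 sets the safety population: "All subjects who are enrolled in the study will be evaluated for safety".

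The analysis is narrower. Section 13.5 consists of two sentences. The first is "The type, severity, duration and frequency of reported ocular adverse events will be tabulated". The second is "Adverse events will also be summarized for events that were considered treatment-related".

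Section 13.3.1 has the investigator classify each event as related or not related, with a second assessment by the Medical Monitor under the same definitions. Related includes possibly related; not related includes events that are merely unlikely to be related. The synopsis describes a single-arm, open-label study with no masking.

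**The concern.** The planned safety results cover less than the protocol tells sites to collect, and for one class of event the boundary is a judgement. A non-ocular event reaches a planned output only if it is called related. Everyone who makes that call knows that the subject had the study procedure, and there is no control group whose event rate could show whether the calls were reasonable.

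Non-ocular events can matter here. Difficulty driving at night is one of the symptoms that Section 8 names, and a fall or a driving injury would be non-ocular. If such an event were judged not related, it would be missing from every planned safety result, even if it met the criteria for a serious event. Separately, because no output records seriousness, a report stating that there were no serious events could not be checked against the planned tables.

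**Working it through.** The plan states no figure on this point and no formula applies. The check sets what is collected against what is to be reported.

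**Step 1: every place that could supply an adverse-event result.**

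- Section 8 lists the safety measures: change in corrected distance acuity, and satisfaction, quality of vision and visual symptoms. Adverse events are not among them.
- Section 10.1 names a population (all enrolled subjects) but no table.
- Section 10.2 promises descriptive statistics and tests chosen to suit the data, with no adverse-event output.
- Section 13.5 gives the two outputs quoted above.

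Section 13.5 is therefore the whole of the adverse-event analysis plan.

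**Step 2: cross ocular or non-ocular with related or not related.**

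| Event | Judged related | Judged not related |
|---|---|---|
| Ocular | Ocular tabulation and related summary | Ocular tabulation |
| Non-ocular | Related summary | No planned output |

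Three of the four cells have an output. The fourth has none, for serious and nonserious events alike, because no separate output for serious events is planned.

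**Step 3: is seriousness shown anywhere?** The ocular tabulation covers type, severity, duration and frequency. Severity in Section 13.3.1 is a mild, moderate or severe grade. Seriousness in Section 13.3 is a different attribute, defined by outcomes such as death, hospitalisation or disability. A serious ocular event would be counted in the ocular tabulation, and a serious related event in the related summary, but neither would be identified as serious.

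**Step 4: what decides entry to the related summary?** Two people assess causality, and no rule says whose assessment feeds the summary if they differ. The reference point also shifts: Section 13.3.1 asks about relation to the device under investigation, while Sections 13.3 and 13.5 speak of the treatment. The test article in the synopsis is planning software, so these two readings need not give the same answer for an effect of the LASIK procedure.

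**Step 5: size.** The documents give no rate of non-ocular events among the 70 subjects and no indication of what share would be judged not related. The number of subjects affected cannot be derived from them.

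**The case against.** The strongest reply is that little of importance would be lost. Every ocular event is tabulated whatever its cause, and the common side effects in Section 19.1 (glare and halos, dry eye, residual refractive error) are ocular or visual. The visual symptoms are also collected by questionnaire with no causality filter. A non-ocular injury with a reasonable possibility of a link counts as related under Section 13.3.1 and would be summarised. The Medical Monitor gives a second opinion, so the call does not rest on the treating investigator alone. Serious events go to the Medical Monitor within one working day and to the ethics board. Section 13.5 does not say that its two outputs are the only ones, so a further listing would contradict nothing. All of this stands, and it limits the weight of the point. It does not fill the empty cell: individual case reporting is not a study result, and two assessments do not amount to masking.

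Three stronger readings are tempting and are not supported:

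- A reader might infer that causality judgement decides which events are shown in general. It does so only for non-ocular events.
- A reader might infer that unrelated serious events go unseen or uncounted. They are reported individually, and an unrelated serious ocular event is counted in the ocular tabulation, though not flagged as serious.
- A reader might infer that the plan fails to support a bound on the serious-event rate. With no events in 70 subjects, the exact two-sided 95% upper limit would be 1 − 0.025^(1/70) = 5.1%, but the protocol does not set out to estimate such a rate, so no stated aim is missed.

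**Conclusion.** The point holds in limited form. Non-ocular adverse events judged not related, serious ones included, have no planned result although the protocol requires their collection, and no planned output identifies any event as serious. This rests on reading Section 13.5 as the complete list of adverse-event outputs, which follows from the absence of any other in the document rather than from an explicit restriction. The primary outcome, residual refractive cylinder, is unaffected. The weight is modest: this is a cheap improvement that brings the reported safety results into line with the protocol's own collection rules. It is not evidence that safety events would be concealed.

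**What to change.** Keep both existing outputs in Section 13.5, including the type, severity, duration and frequency of ocular events, and add:

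> All AEs will be summarised for all enrolled subjects by ocular or non-ocular type, severity and relationship, whatever the causality assessment. All SAEs, related and unrelated, will be listed separately, showing both the investigator's and the Medical Monitor's causality assessment.

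Showing both assessments in the listing means that no rule is needed there on which one prevails. For the related summary, one added sentence should say whose assessment is used.

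The events are already recorded on study forms and both causality assessments are already required, so no visit, procedure or form is added. The cost is one or two extra tables for 70 subjects. The downside is that they will include incidental illness unconnected with the surgery.
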